Due to the overwhelming burden on the healthcare system and high transmissibility of the virus, patients who may have typically been treated in a hospital were followed at home until absolutely necessary. These patients are suffering from longterm adverse consequences of COVID-19 and would greatly benefit from a rehabilitative intervention. Therefore, we are broadening our inclusion criteria to include any patient who visited the ED for COVID or was hospitalized for any length of time due to COVID symptoms (both typically for hypoxia and shortness of breath).

A1. Study Objectives/Hypotheses.

COPD Patients

Objective 1. To determine the efficacy of a 12-week, home-based, patient-tailored, RAS-enhanced music exercise program in improving functional and clinical parameters in COPD.

Hypotheses: Compared to patients randomized to a home-based, exercise program without music (control group), patients randomized to a home-based, exercise program augmented with RAS-enhanced music (experimental group; hereafter referred to as RAS-music group) will demonstrate greater:

1a-increase in 6-minute walking distance (primary hypothesis);

1b-greater increases in health-related quality of life (QoL).

Objective 2. To determine whether at 12 weeks the RAS-music group will accumulate a greater volume of daily physical activity than the control group.

Hypothesis: The RAS-music group will accumulate a greater volume of daily physical activity than the control group. This will be demonstrated by greater physical activity at 12 weeks (actigraphy).

Objective 3. To determine whether, 24-weeks after randomization, gains in 6-minute walk distance and perceived functional improvements will be sustained to a greater extent in the RAS-music group than in the control group.

Hypothesis: The RAS-music group will maintain improvements in measured and perceived function at 24 weeks to a greater extent than the control group.

Objective 4. To assess impact of physiological and psychological phenotype and clinical factors on responsiveness to rehabilitation achieved with and without concurrent use of RAS-music (Exploratory Objective).

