A.3.2.2. Exercise-Training: Hospital-Based vs. Home-Based Programs. Hospital-based pulmonary rehabilitation can produce favorable structural adaptations in the locomotor muscles and improve the clinical status of patients with COPD.^{3,4,6,9} Unfortunately, less than 5% of patients who would benefit from rehab are enrolled in such a program.^{46,47} Limited access of programs,^{8,10} suboptimal compliance¹¹ and transportation difficulties^{10,48} are the most common obstacles for uptake and completion of hospital programs. In addition, the gains achieved during hospital-based programs diminish progressively over time if regular physical activity is abandoned.⁴⁹ Recognition of these drawbacks has triggered interest in home rehab programs.¹¹⁻¹⁵ McGavin et al⁵⁰ were the first to report that unsupervised exercise at home (stair climbing), could reduce dyspnea and improve exercise capacity in 12 patients with COPD. Similar results were later reported by Puente-Maestu et al,¹⁶ Strijbos et al,¹⁵ Wedzicha et al¹² and Hernandez et al.¹³ These investigations, however, have methodological limitations that hamper the generalizability of the results. In Puente-Maestu et al,¹⁶ Wedzicha et al¹² and Hernandez et al.¹³ patients received no external encouragement during exercise. Strijbos et al¹⁵ and Wedzicha et al¹² utilized physiotherapists to supervise home-exercise training – a prohibitive resource-intensive strategy for most health care systems. As for the study of Hernandez et al,¹³ the training prescription was nebulous and sample size small (20 patients in intervention group and 17 in control group completed the study). This factor raises the spectrum of Type II error. All these limitations will be overcome in the current investigation.

In a departure from previous strategies, Liu et al¹¹ developed a home-based program where 24 patients

with

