• Mean SpO ₂ ≥ 88% at peak exercise (with or without oxygen supplementation)	• Stops exercise for arthritic pain in knee or hips
• Ability to hear music	• Inability to walk on the treadmill
	• Any unforeseen illness or disability that would preclude exercise testing or training
	• Participation in a formal exercise program within the previous 12-weeks

Liu et al.,¹¹ we estimate no change in the 6MWT in the no-music exercise training group.

COVID 19 sample size was estimated based on a 2-group design with pre- and post-test measurements. Our primary goal is to compare the difference in distance walked during the *standard 6MWT* at 12 weeks between groups. We estimate that over a two-year period we will ensure complete data collection on a total of 72 patients (36 per group). This will ensure a 58% power to detect the differences between treatment arms using a two-sided significance level of 0.05, assuming a correlation of 0.65 between measurements. Our pilot data used to support this estimate include the most conservative correlation observed between measurements ($r=0.65$), and an increase of 41 meters at 12 weeks for the intervention group.

According to the local IRB, enrollment is the equivalent to a patient signing an informed consent. In our three latest studies,^{3,4,94} 30% of patients who signed the informed consent (i.e., enrollees) did not meet pulmonary function criteria or did not qualify for other reasons.⁹⁵ Moreover, based on our previous work, we expect an attrition 12 weeks after randomization of about 8%, and an attrition 24 weeks after randomization of 20%. Accordingly, to have complete data in 136 COPD patients as required by our power calculation (see above), we plan to 'enroll' 243 COPD patients (i.e., signed informed consent) expecting to 'randomize' 170 of them, and to lose 34 of this latter group by week 24 (end of the study). We will enroll 100 patients with COVID 19 into this study.

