H1A: IN PATIENTS WITH COPD, IMPROVEMENTS IN 6-MINUTE WALKING DISTANCE WILL BE GREATER AFTER COMPLETING 12 WEEKS OF A HOME-BASED, EXERCISE PROGRAM WITH RAS-ENHANCED MUSIC THAN AFTER A HOME-BASED, EXERCISE PROGRAM WITHOUT MUSIC.

The analysis of the primary outcome (improvements in 6-minute walking distance) is based on all data collected during the intervention period—baseline, 6 and 12-weeks. We will use a mixed-model analysis that includes treatment, time and treatment-by-time interaction terms. Specifically, we will test whether the treatment- by-time interaction differs from 0. This model will automatically account for missing data

where missing at random is assumed. We will conduct a sensitivity analysis^{129,130} based on the results of the mixed model analysis to determine whether other assumptions regarding the missing data may produce different results. One component of the sensitivity analysis will also include adjustment for

baseline demographic and health covariates.

C.2.2. Statistical Analysis: Secondary Hypotheses

Statistical analysis for H_{1c} will parallel that of H_{1a} .

H_{1D} : THE RAS-ENHANCED MUSIC GROUP WILL DEMONSTRATE GREATER INCREASES IN HEALTH-RELATED QUALITY OF LIFE (QOL) THAN THE CONTROL GROUP.

Statistical analysis for H_{1d} will parallel that of H_{1a} .

H_2 : THE RAS-ENHANCED MUSIC GROUP WILL ACCUMULATE A GREATER VOLUME OF DAILY PHYSICAL ACTIVITY THAN THE CONTROL GROUP. THIS WILL BE DEMONSTRATED BY GREATER PHYSICAL ACTIVITY AT 12 WEEKS (ACTIGRAPHY).

Statistical analysis for H_2 will parallel that of H_{1a} .

H_3 : THE RAS-ENHANCED MUSIC GROUP WILL MAINTAIN IMPROVEMENTS IN MEASURED AND PERCEIVED FUNCTION AT 24 WEEKS TO A GREATER EXTENT THAN THE NO-MUSIC CONTROL GROUP.

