In the statistical analysis of H_3 , we will use independent t-tests to compare the changes in measured function (distance walked in the 6MWT and perceived function (questionnaires) between 12 and 24-weeks between the RAS-music and the no-music groups. We will also conduct paired t-tests within each group to determine whether values at 24 weeks are worse than those at 12 weeks. These computations will be based on those patients with 12 and 24-week data. To assess whether patients included in the H_3 analysis are representative of the original randomized groups, we will also compare demographic and health measures (i.e., FEV₁ percent predicted, comorbidities, depressive symptoms and exacerbations) of patients included in the H_3 analysis to patients who were not.

C.2.3. Statistical Analysis: Exploratory objective: [exploratory objective not reported]

TO ASSESS IMPACT OF PHYSIOLOGICAL AND PSYCHOLOGICAL PHENOTYPE AND CLINICAL FACTORS ON RESPONSIVENESS TO REHABILITATION ACHIEVED WITH AND WITHOUT CONCURRENT USE OF RAS-MUSIC. PHYSIOLOGICAL FACTORS INCLUDE: SYSTEMIC INFLAMMATION (HS-CRP), QUADRICEPS STRENGTH, RECRUITMENT AND FATIGUE, QUADRICEPS FUNCTION AND DIMENSION AFTER REHABILITATION. PSYCHOLOGICAL FACTORS INCLUDE: SELF-EFFICACY, ANXIETY AND DEPRESSION. CLINICAL FACTORS INCLUDE: ADHERENCE TO THE 12-WEEK PROGRAM, ADHERENCE TO FOLLOW-UP AND NUMBER AND SEVERITY OF EXACERBATIONS.

To assess the impact of the above confounders two separate analyses will be conducted: (a) A linear regression model with changes from baseline to 12 weeks of training as the dependent variable, and assigned treatment group, physiologic and psychologic phenotype and clinical factors as the independent variables, and

(b) A mixed model ANOVA with baseline, and 12 and 24 weeks measurements as dependent measures and assigned group, physiologic and psychologic phenotype and clinical factors as the independent variables.

C.3. Expected Outcome: We expect to demonstrate that improvements in 6-minute walking distance from baseline to 12 weeks will be greater after completing 12 weeks of a home-based, exercise program with RAS- music than after a home-based, exercise program without music.

C.4. Alternative Outcomes. Our primary hypothesis will be rejected if, at 12 weeks, improvements in 6-minute walking distance are not greater with exercise-training plus RAS-music than with exercise-training without music. In this case, at least three alternative outcomes will be considered.

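### H3 tests sustained gains only through the 12-to-24-week change, so no stated primary or secondary test compares the arms on gain from baseline at 24 weeks

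*Combined protocol and SAP*

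**What the plan says.** Section A1, Objective 3, asks whether at 24 weeks "gains in 6-minute walk distance and perceived functional improvements will be sustained to a greater extent in the RAS-music group" compared with controls. C.2.2 restates this as H3: the RAS group will "MAINTAIN IMPROVEMENTS IN MEASURED AND PERCEIVED FUNCTION AT 24 WEEKS TO A GREATER EXTENT THAN THE NO-MUSIC CONTROL GROUP".

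The H3 analysis in C.2.2 has two parts. Between arms, "we will use independent t-tests to compare the changes in measured function" and perceived function from week 12 to week 24. Within each arm, paired t-tests ask whether week 24 is worse than week 12. On the analysis set, the plan states: "These computations will be based on those patients with 12 and 24-week data". It adds a comparison of the characteristics of patients included in and left out of H3.

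Other analyses that might cover week 24:

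- The H1a mixed model (C.2.1) is "based on all data collected during the intervention period—baseline, 6 and 12-weeks". The remaining H1 analyses and H2 are said to parallel it.
- The exploratory objective (C.2.3) includes "A mixed model ANOVA with baseline, and 12 and 24 weeks measurements as dependent measures", with assigned group, phenotype and clinical factors as independent variables.

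For the 12-week sample size (C.1.3), the plan states: "we estimate no change in the 6MWT in the no-music exercise training group".

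**The concern.** A gain is measured from baseline, but baseline does not enter H3. The planned contrast starts at week 12, when a successful programme will already have separated the arms. An arm that has gained more has more to lose, and a comparison of later change alone counts that against it.

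The plan's own background makes some loss plausible: A.3.2.2 says "the gains achieved during hospital-based programs diminish progressively over time if regular physical activity is abandoned". If RAS-music works and part of its effect fades, H3 can report no difference, or significantly worse maintenance, while RAS patients still walk further than controls. A reader would then conclude that the benefit did not last, when the analysis never asked whether any benefit remained.

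The exploratory model does not fill the gap. Its purpose is to assess confounders, it names no group-by-time term or 24-week group contrast, and it adjusts for factors that arise after randomisation, such as adherence, exacerbations and quadriceps function after rehabilitation.

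**Working it through.** **Inputs from C.1.3 (COPD).** RAS gain 87.2 ft at 6 weeks (slightly higher at 12 weeks, amount not given); control change 0; SD 232 ft; r = 0.70; two-sided 0.05; 68 per arm. The 68 also applies at week 24: 170 randomised less 34 lost leaves 136.

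**Assumed here.** The same SD and r for later intervals, 87.2 ft as the week-12 gain, and every figure for retention, control gain or loss, and further divergence.

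**Reproducing the plan's figure.** SD of change = 232 × √(2 × (1 − 0.70)) = 179.7 ft. Detecting 87.2 ft with 80% power needs 68 per arm by the t-test; power at 68 is 80.2%. This matches the plan.

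**Standard errors.**
- Difference in change: 179.7 × √(2/68) = 30.8 ft.
- Baseline-adjusted difference: 232 × √(1 − 0.70²) × √(2/68) = 28.4 ft.

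**The two contrasts, with equal baselines.**
- Planned: (RAS24 − RAS12) − (C24 − C12).
- Missing: RAS24 − C24.

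**General result.** Let the week-12 gains be G_R and G_C, with both arms keeping a fraction f. The planned contrast is (f − 1)G_R − (f − 1)G_C = −(1 − f)(G_R − G_C). The missing contrast is f(G_R − G_C). For any f between 0 and 1 the two have opposite signs. Flat controls are not needed.

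**Probabilities** (noncentral t, 134 df; power of the missing contrast is shown as change score, then baseline-adjusted):

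| Scenario | Planned, ft | Significant for RAS | Significant against RAS | Missing, ft | Power of missing contrast |
|---|---|---|---|---|---|
| 1. Controls flat, RAS keeps 100% | 0 | 2.5% | 2.5% | 87.2 | 80% / 86% |
| 2. Controls flat, RAS keeps 75% | −21.8 | 0.4% | 10% | 65.4 | 56% / 63% |
| 3. Controls flat, RAS keeps 50% | −43.6 | <0.1% | 29% | 43.6 | 29% / 33% |
| 4. RAS gains 130.8, controls 43.6; both keep 75% | −21.8 | 0.4% | 10% | 65.4 | 56% / 63% |
| 5a. RAS gains a further 43.6, or flat controls then fall 43.6 | +43.6 | 29% | <0.1% | 130.8 | 99% / >99% |
| 5b. Controls gain 43.6 and lose it all; RAS keeps 75% of 87.2 | +21.8 | 10% | 0.4% | 65.4 | 56% / 63% |

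A simulation of 20,000 trials agrees. Scenario 2 gave 0.3% for RAS, 10.4% against and 55.8% power for the missing contrast; scenario 3 gave 29.0% against and 28.8% power.

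**Divergence needed.** For 80% power the planned test needs (1.96 + 0.84) × 30.8 = 86 ft of further separation after week 12, about the whole assumed programme effect again.

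**Sensitivity to r.** At the pilot correlations of 0.76 to 0.86 (standard errors 27.6 to 21.1 ft), the chance of significance against RAS is 12 to 18% in scenario 2 and 35 to 54% in scenario 3. If the correlation over the longer baseline-to-24-week interval were only 0.60 (assumed), power of the missing contrast as a change score would fall to 68% in scenario 1 and 45% in scenario 2 (53% adjusted).

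**The case against.** The strongest reply is that maintenance can mean loss after the programme, and the planned test measures exactly that. If RAS patients lose more feet after week 12, saying so is correct, and 2.5% in scenario 1 is simply the test's error rate when neither arm lost anything. This stands: the 12-to-24-week change is a valid measure and should stay. It does not answer whether gains remain, which Objective 3 also asks.

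Second, flat controls after week 12 are not a plan input. The no-change figure concerns the 12-week 6MWT and does not cover the questionnaires, and the Potential Benefits section allows controls to gain because they also exercise. This is fair as regards scenarios 1 to 3, but the general result and scenario 4 do not depend on it.

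Third, the plan has reasons to expect divergence in favour of RAS. The music is recalibrated at week 12 for optional later use (C.1.6.1), A.4 expects benefits to be maintained through continued use, and A.3.3.3 cites a home programme after which patients improved further. Scenarios 5a and 5b allow for this. The planned test can then favour RAS, but with only 10 to 29% probability, against 56 to 99% for the 24-week contrast as a change score. These percentages concern different quantities, so they show what each test can detect and do not rank two tests of one hypothesis.

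Fourth, a rough 24-week estimate could be pieced together from the 12-week difference and the later change. It would come without a planned test or interval.

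**Conclusion.** The concern holds. No stated test for a primary or secondary hypothesis compares the arms on gain from baseline at 24 weeks, and the exploratory model does not supply that comparison. When both arms keep the same fraction of their gain, short of all of it, H3 is expected to go against the arm that gained more.

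With the plan's inputs and flat controls, a 65.4 ft remaining advantage gives a 10% chance of a significant result against RAS and 0.4% in its favour. At 43.6 ft the figures are 29% and under 0.1%. The direction H3 will actually take is uncertain, because retention, control behaviour after week 12 and the later correlations are all assumed. That the contrast is missing does not depend on those assumptions.

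Restricting H3 to patients with both visits also leaves out about 34 of 170 randomised patients; no bias from this has been quantified. H3 is secondary, and the primary test and sample size are unaffected. This should be fixed.

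**What to change.** - Extend the H1a mixed model to include week 24, using all randomised patients with any 6MWT measurement. Name the baseline-adjusted between-arm difference at week 24 as the test of whether gains are sustained. Do the same for the questionnaires.
- Keep the 12-to-24-week independent and paired t-tests, labelled as measures of loss after the programme and reported with each arm's week-12 gain.
- State the order of interpretation: first the 24-week contrast (does a benefit remain?), then the 12-to-24-week change (how much was lost?).
- Keep the comparison of included and excluded patients, to inform the missing-at-random assumption.

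The 6MWT and questionnaires are already collected at baseline and week 24, so no new visits, data or patients are needed. The cost is SAP wording, one more secondary contrast per H3 outcome, and a stated order of interpretation.

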In the investigations of Burtin et al⁴⁴ and Mador et al,⁴⁵ quadriceps fatigue was objectively quantified by recording decreases in force of knee extension elicited by single magnetic stimulations of the femoral nerve (quadriceps twitch or Quad-Tw)(**Fig. 2**). We have extensively used this state-of-the-art technique to evaluate strength and fatigue in healthy volunteers, patients with COPD and mechanically ventilated patients.¹³¹

We will collect data on quadriceps fatigability at the end of training (Quad-Tw). Specifically, we will determine whether randomization into RAS-music will increase the likelihood of quadriceps fatigue and whether quadriceps fatigue contributes to the beneficial effects of the home-based, RAS-music exercise program. These data will be used also to explore whether there are specific subgroups of patients who – in addition to RAS-enhanced exercise-training – could benefit from specific ancillary interventions (see sections **C.4. Alternative Outcomes** and **C6. Future Directions**).⁴¹

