In contrast to the previous studies, Strijbos et al¹⁵ were successful in maintaining (and indeed improving) pulmonary rehab gains following 12 weeks of home-care rehabilitation. The investigators speculate that patients had become accustomed to exercise in their own domiciliary environment. This made it easier for them to continue exercising at home after the initial 12-weeks of training were over. A similar result was recently reported in the small proof-of-principle study of Ho et al.⁵⁸

The observations of Strijbos et al¹⁵ and Ho et al.⁵⁸ combined with our success in increasing exercise performance with RAS-enhanced music (see *preliminary results*, **Section B.6.1.**) lay the scientific foundation of the proposed experiments in our *Objective #3*. Specifically, these observations raise the possibility that combining RAS-music and home-based exercise training will result in greater long-term maintenance of rehabilitation gains than exercise-training alone.

A.3.4. Potential Confounders. Potential confounders to any pulmonary rehabilitation study include the patients' physiological and psychological phenotype and clinical factors.

A.3.4.1. Potential Confounders: Physiological Phenotype. Decreased exercise tolerance with attendant difficulty in achieving sufficient intensity of exercise during training hinders the effectiveness of rehab.⁶³ In addition to severity of lung disease, independent predictors of decrease exercise tolerance include quadriceps dimension, recruitment and strength, systemic inflammation (hsCRP and IL-6)⁶⁴ (see *work accomplished*).

A.3.4.2. Potential Confounders: Psychological Phenotype. Depression,^{49,60,65} anxiety^{49,60,65} and overall sense of fatigue^{62,66} can limit the effectiveness of pulmonary rehab as these factors may cause insufficient adherence to rehabilitation programs.

A.3.4.3 Potential Confounders: Clinical Factors. Approximately 15% of patients drop out from pulmonary rehab due to clinical factors such as COPD exacerbations,⁶⁷ cardiovascular disease (myocardial infarction, cerebrovascular accidents), or cancer.⁶⁸ Because of this, in the proposed investigation, we will assess the influence of the physiological and psychological phenotype and clinical factors on the effectiveness of RAS- enhanced and non RAS-enhanced home-based

rehabilitation (*Objective #4*).

A.4. Significance and Relevance to the VA.

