The resulting effect of this integrated synergy will be to promote greater functional gains (primary hypothesis) at the end of 12 weeks of home- based exercise training and to promote better maintenance of the benefits of pulmonary rehab at 24 weeks than in the no-music group (secondary hypothesis).

C.1.2. General Overview of Design. The proposed study has been designed as a randomized, controlled clinical trial in which COPD patients will be randomized into an exercise program with RAS-enhanced music (RAS- music group) or in an exercise program without music (no-music group). COVID 19 patients will be randomized into an exercise program with RAST-enhanced music (RAST- music group and strength training) or in an exercise program without music (no-music but will have strength training group). Patients will complete testing procedures at pre-randomization, at 6 weeks, immediately post-rehabilitation, and 24 weeks after enrollment. Testing at 6 weeks is included to provide interim follow-up should patients not complete the 12 weeks of training.

C.1.3. Sample Size Calculation.

Sample size was estimated based on a 2-group mixed model design with baseline, 6 and 12-week measurements. Our primary goal is to compare the difference in distance walked during the standard 6MWT over 12 weeks between groups (see **C.1.9.1.a.**). We estimate that the COPD target sample size of 68 patients per group completing 12 weeks will ensure 80% power to detect the differences between treatment arms using a two-sided significance level of 0.05, assuming a correlation of 0.70 between measurements. These estimates are based on our PAD pilot data and include similar standard deviations at baseline and at 6 weeks between groups and over time (232 feet), correlations between measurement of 0.76 to 0.86, and an increase of 87.2 feet at 6 weeks for the RAS- music group, with a slightly higher level for those completing the 12-week assessment. Based on the work of

Table. 2 COPD Study inclusion and exclusion criteria

Inclusion Criteria	Exclusion Criteria
• ≥ 40 yr. of age	• Respiratory infection/COPD exacerbation within the previous four weeks
• FEV ₁ ≤ 70%	• Exercise-limiting heart disease (Congestive heart failure – i.e., New York Heart Association Class III or IV; positive stress test or other indicators of heart disease or complaints of angina during the stress test)
• FEV ₁ /FVC <70%	• Exercise-limiting peripheral arterial disease (stops walking due to intermittent claudication)

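### The Objective 4 models name no group-by-factor term, so they cannot show whether a factor's association with response differs with and without RAS-music

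*Combined protocol and SAP*

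**What the plan says.** Section A1 states Objective 4 for the COPD cohort, marked exploratory, as: "To assess impact of physiological and psychological phenotype and clinical factors on responsiveness to rehabilitation achieved with and without concurrent use of RAS-music". Section A.3.4.3 restates the aim as assessing "the influence of the physiological and psychological phenotype and clinical factors on the effectiveness of RAS- enhanced and non RAS-enhanced home-based" rehabilitation. Section A.3.2.1 asks a question specific to one arm: "whether quadriceps fatigue contributes to the beneficial effects of the home-based, RAS-music exercise program".

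Section C.2.3 gives two models. Model (a) is a linear regression of the change from baseline to week 12 on "assigned treatment group, physiologic and psychologic phenotype and clinical factors as the independent variables". Model (b) is a repeated-measures ANOVA in mixed-model form, specified as: "baseline, and 12 and 24 weeks measurements as dependent measures and assigned group, physiologic and psychologic phenotype and clinical factors as the independent variables". No group-by-factor term, within-arm model or subgroup analysis is named for this objective. Model (b) also names no time term.

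The primary analysis in C.2.1, by contrast, spells out its terms: "We will use a mixed-model analysis that includes treatment, time and treatment-by-time interaction terms".

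**The concern.** Whether a factor acts differently in the two programmes is a question about effect modification. In a regression it is answered by a group-by-factor term, or by separate estimates in each arm. C.2.3 provides neither. Because C.2.1 does name its interaction, the omission in C.2.3 is hard to read as shorthand. C.2.3 also introduces the factors as confounders, which is the language of adjustment.

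What is at stake is how the results feed later work. A.3.1.2 and A.3.2.1 say the muscle data will be used to look for subgroups who might need ancillary interventions on top of RAS training. C.6 would base a follow-on study on whether patients in RAS-music rehabilitation need to develop quadriceps fatigue in order to benefit. If the arm-specific terms are not written down in advance, either the question goes unanswered or the subgroups are chosen after the data are seen.

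**Working it through.** **Inputs (C.1.3).** SD of 6MWT distance 232 ft; correlation 0.70; planned effect 87.2 ft, with no change in controls; 68 per group; two-sided 0.05; 80% power.

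**Assumptions not in the documents.** The dependent variable in C.2.3 is 6MWT distance (the section does not name it). A factor has the same distribution in both arms. A continuous factor is scaled to SD 1. A binary factor has share q, varied below.

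**Step 1: reproduce the plan's figure.** The plan states "COPD target sample size of 68 patients per group completing 12 weeks will ensure 80% power".
- SD of change = 232 × √(2 × (1 − 0.70)) = 179.7 ft.
- n per group = 2 × (1.960 + 0.842)² × (179.7 / 87.2)² = 66.7, so 67 by the normal approximation.
- With the noncentral t, 68 is the first n to reach 80% (80.2%).

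The stated size reproduces on a change score, so 179.7 ft is a fair scale for model (a).

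**Step 2: what model (a) estimates.** With equal arms and no product term, the fitted factor coefficient is the average of the two arm-specific effects, (control + RAS) / 2. The table shows 4,000 simulated trials per row, 68 per arm, with a binary factor split 50/50.

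| True factor effect, control / RAS (ft) | Model as listed: mean coefficient, % with p<0.05 | Product term added: mean interaction, % with p<0.05 |
|---|---|---|
| +43.6 / +43.6 | 43.8, 29% | 0.2, 6% |
| 0 / +87.2 | 43.8, 29% | 85.9, 29% |
| −43.6 / +43.6 | −0.6, 5% | 88.1, 29% |
| −87.2 / +87.2 | 1.0, 5% | 174.1, 80% |

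Rows 1 and 2 are the main result: a common effect and a purely RAS-specific one give the same coefficient. This is a failure to identify the contrast, and a larger sample would not cure it. Rows 3 and 4 show that opposite effects cancel.

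**Step 3: illustrations with a continuous factor.** These are not expectations.
- Slopes of −60 (control) and +60 (RAS) ft per SD, 2,000 simulated trials: the listed model averages −1.2 ft and flags the factor in 6.4%; the interaction averages 119.6 ft and is detected in 96%.
- Slopes of 0 and +60 ft per SD: the pooled slope is 30 ft with SE 179.7 / √136 = 15.4 ft; the interaction is 60 ft with SE 30.8 ft. Both ratios are about 1.95, so power is about 50% for each. The listed model flags the factor as often but cannot say in which arm it acts.

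**Step 4: what model (b) estimates.** As listed, a factor with coefficient γ adds γ at baseline, week 12 and week 24 alike. In the difference between week 12 and baseline, γ cancels. It therefore describes average walking level. Adding time and group-by-time does not change this: the modelled change then depends on group and time, still not on the factor. Response needs factor-by-time, and response by arm needs group-by-factor-by-time.

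**Step 5: precision if the product term is added to model (a).**
- Continuous factor: SE = 2 × 179.7 / √136 = 30.8 ft per SD; detectable with 80% power = 2.80 × 30.8 ≈ 86 ft per SD.
- Binary factor: SE = 179.7 × √(2/68) × √(1/q + 1/(1−q)). At q = 0.50, SE is 61.6 ft, power for 87.2 ft is 29%, and the detectable interaction is 173 ft. At q = 0.33: 65.5 ft, 27%, 184 ft. At q = 0.20: 77.0 ft, 20%, 216 ft.
- An 87.2 ft interaction at q = 0.50 would need about 267 per group.
- With 8% attrition at week 12, 170 × 0.92 ≈ 156 patients contribute: SE 28.8 ft per SD, detectable 81 ft per SD, and binary power at q = 0.50 of 33%.
- Adjusting for baseline instead of using change gives residual SD 232 × √(1 − 0.70²) = 165.7 ft, SE 2 × 165.7 / √136 = 28.4 ft per SD, and detectable about 80 ft per SD with 136 patients.

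**The case against.** Six points deserve weight.

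- **The main-effects reading is inferred.** C.2.3 lists independent variables, not model terms. A repeated-measures mixed ANOVA normally carries time and group-by-time. This stands for model (b). A reader might infer that model (b) shrinks the treatment effect by averaging in the pre-randomisation baseline. That holds only if time and group-by-time are both absent, which the documents do not say. Convention does not, however, supply a factor-by-time or group-by-factor term.
- **Model (a) does address a form of the objective.** Its outcome is change, so a factor's coefficient is an association with response. If the objective means response in either programme, the pooled estimate answers it. A reader might therefore go too far in concluding that neither model estimates what Objective 4 asks. What the models miss is the comparison by arm, to which A.3.2.1 and A.3.4.3 point.
- **Most stated uses do not need an interaction.** C.4.1 concerns imbalance between arms, C.4.3 concerns factors limiting both groups, and failure to entrain to music has no control-arm counterpart. This stands. The arm-specific questions in A.3.2.1 and C.6 remain.
- **A crossover is a worst case.** The −60/+60 ft illustration implies a 120 ft per SD difference, more than the whole planned effect of 87.2 ft, and nothing in the documents suggests it. It shows the mechanism only.
- **A product term does not suit every factor.** Adherence, exacerbations and quadriceps measures after rehabilitation arise after randomisation; C.1.6.1 schedules Quad-Tw at week 12 only. Interactions with these are not effect modification. This stands and shapes the fix.
- **The objective is exploratory.** It carries no power claim, and the C.2.3 heading has a note that the exploratory objective is not reported. The meaning of that note is unclear, but the objective and models remain in the current text.

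**Conclusion.** The point holds in limited form. As listed, model (a) gives pooled associations with 12-week change and cannot separate a common factor effect from an arm-specific one. Model (b), even with time and group-by-time taken as understood, gives factor effects on average level rather than on response.

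The identification point in model (a) does not depend on the SD or the sample size. It needs only that no group-by-factor term is fitted, which is read from the list of variables and supported by the contrast with C.2.1. The precision figures rest on the C.1.3 inputs and on an assumed factor distribution, and apply to the COPD cohort only. They show that naming the right terms will make the question answerable in principle but not precisely: about 86 ft per SD is needed for 80% power, and an interaction as large as the planned treatment effect has 20% to 29% power across the splits examined.

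Nothing here touches the primary analysis or the sample size.

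**What to change.** Revise C.2.3 as follows.

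1. Name a short, pre-specified list of factors measured at baseline.
2. Model (a): add group-by-factor for each, with baseline 6MWD as a covariate.
3. Model (b): state time, group-by-time, factor-by-time and group-by-factor-by-time, and read the contrasts at weeks 12 and 24.
4. Report estimates with 95% confidence intervals, labelled exploratory, and state the expected imprecision.
5. Analyse adherence, exacerbations and post-rehabilitation quadriceps measures separately, as within-arm associations, and do not present them as effect modifiers. The quadriceps fatigue question in A.3.2.1 belongs here.
6. If only the pooled question is intended, reword Objective 4 and the A.3.4.3 restatement to say so, and still add factor-by-time to model (b). If the analysis has been dropped, say that.

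The cost is SAP wording and a little more analysis, using data already planned. The downside is wide intervals, with the risk that a chance finding is over-read; the short list and the exploratory label are there to contain that.
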